## LIST OF ABBREVIATIONS

AE	Adverse Event
COMP	Cartilage Oligomeric Matrix Protein
DCC	Data Coordinating Center
DHHS	DHHS Department of Health and Human Services
DSMB	Data Safety Monitoring Board
FDA	FDA Food and Drug Administration
GCP	GCP Good Clinical Practice
GLP	GLP Good Laboratory Practices
HIPAA	HIPAA Health Insurance Portability and Accountability Act
IND	Investigational New Drug Application
IRB	Investigational Review Board
MOP	Manual of Procedures
NIH	NIH National Institutes of Health
OHRP	Office for Human Research Protections
PI	Principal Investigator
PSACH	Pseudoachondroplasia
SAE	Serious Adverse Event
SMC	Safety Monitoring Committee
SOP	Standard Operating Procedure
UP	Unanticipated Problem
US	United States
CI	Co Investigator

## STATEMENT OF COMPLIANCE

The trial will be carried out in accordance with Good Clinical Practice (GCP) as required by the following (*use applicable regulations depending on study location and sponsor requirements; examples follow*): United States (US) Code of Federal Regulations (CFR) applicable to clinical studies (45 CFR Part 46, 21 CFR Part 50, 21 CFR Part 56, 21 CFR Part 312, and/or 21 CFR Part 812) ICH E6

All key personnel (all individuals responsible for the design and conduct of this trial) have completed Human Subjects Protection Training.

## PROTOCOL SUMMARY

[figure not shown]
Title:	Trial of Resveratrol for Pseudoachondroplasia Pain
Précis:	This is a cross over designed study to determine if self-administered oral resveratrol (90 days) can dampen joint pain for individuals with pseudoachondroplasia compared to placebo (90 days) as measured by daily pain logs.
Objectives:	To determine if resveratrol reserveage liquid lessens joint pain in individuals with pseudoachondroplasia.
Endpoint	Self-reported pain as ascertained by a 11-point pain scale from 0 to 10.
Population:	Pseudoachondroplasia patients aged 18 to 70 yrs (details below)
Phase:	IIA ("proof of concept" study)

**Number of Sites enrolling participants:** 1  
**Description of Study Agent :** Resveratrol Reserveage liquid super berry blend 225 mg + Pro-longevity factors blend 130 mg including **125 mg trans-resveratrol**

**Study Duration:** 5 yrs  
**Participant Duration:** 210 days

## 2 INTRODUCTION: BACKGROUND INFORMATION AND SCIENTIFIC RATIONALE

### 2.1 BACKGROUND INFORMATION

Pseudoachondroplasia (PSACH), a severe short-limb dwarfing condition, results from mutations that cause misfolding of the cartilage oligomeric matrix protein (COMP). Accumulated COMP in growth plate chondrocytes activates cellular stress that leads to inflammation and oxidative stress, ultimately causing chondrocyte death. The most debilitating features of the disorder is childhood joint pain and severe early-onset osteoarthritis. The only treatments for this pain are sporadic NSAID administration and joint replacement. We have shown that resveratrol dampens chondrocyte inflammation in a mouse model of the disorder. Given the lack of specific treatment for PSACH, the positive results with resveratrol in the mouse model and the low risk of resveratrol treatment, we propose to test resveratrol to treat joint pain in PSACH.

### 2.2 RATIONALE

We have shown, in a mouse model of PSACH, that resveratrol reduces chondrocyte inflammation and improves the health and longevity of chondrocytes. This work was the first and only therapeutic approach shown to mitigate both the chondrocyte and long-bone pathology of PSACH in a mouse model and suggests that reducing inflammation and oxidative stress early in the disease process with resveratrol may be a novel approach to treat this disorder. Additionally, other researchers have shown that resveratrol reduces joint damage in mouse models of arthritis. Taken together these observations suggest that resveratrol may be beneficial for PSACH joint pain. In addition, resveratrol is available over the counter and has not been associated with major adverse events suggesting that the risk associated with resveratrol are low.

## 2.3 POTENTIAL RISKS AND BENEFITS

### 2.3.1 KNOWN POTENTIAL RISKS

Four clinical trials have shown mild to moderate adverse gastrointestinal side effects associated with high levels of resveratrol 0.5- 5 g/day. and Resveratrol for Alzheimer's disease at clinicaltrials.gov. The longest safety study was a 52 week phase II study of dosages up to 2 g/day for adults, the incidence of nausea and diarrhea were no different between placebo and resveratrol groups. This phase II trial of 119 participants administered pure synthetic resveratrol 500 mg orally once daily with a dose escalation by 500-mg increments every 13 weeks until a final dose of 1000 mg twice daily was reached for the final 13 weeks concluded "Resveratrol (1) is detectable in cerebrospinal fluid (at low nanomolar levels), (2) **is safe and well tolerated**, (3) alters AD biomarker trajectories, (4) preserves blood-brain barrier integrity, and (5) modulates the CNS immune response". **This 52 week safety trial shows that resveratrol is safe to use in humans for an extended period of time at dosages above those used in our study.** Additionally, resveratrol is available over the counter and has not been associated with major adverse events, suggesting that the risk associated with resveratrol is low. Previous studies in adults have used resveratrol dosages ranging from 40 mg - 5 g. There are at least 100 resveratrol clinical trials and many studies did not show or discuss adverse events. Four clinical trials showed mild to moderate adverse gastrointestinal side effects associated with high levels of resveratrol 0.5- 5 g per day and (<https://clinicaltrials.gov/ct2/show/results/NCT01504854?term=resveratrol&cond=Alzheimer+Disease&rank=1&search=1>). Our study dosage at 125 mg/day for adults is far below this range

Category	Summary of findings	Reference
Common adverse events	
 
- mild to moderate adverse gastrointestinal side effects
 
- In the largest (n = 119), longest (52 weeks), and highest-dose (ending with 2 g by mouth daily) human study of resveratrol to date, a total of 104 participants completed the phase II study. Inclusion criteria individuals >49 years old with a diagnosis of mild-to-moderate dementia due to AD, with stable medications and medically stable. No differences were found between the resveratrol and placebo-treated groups in terms of safety and tolerability, with the only exception being weight loss in the resveratrol-treated group. The most common reported AEs were nausea and diarrhea, with 42% reported in the resveratrol group versus 33% in the placebo group. The difference between groups was not statistically significant different. The high background of gastrointestinal AEs is likely due to concomitant treatment with a cholinesterase
 
	12,10,11,14

	inhibitor approved for Alzheimer disease. Weight loss in the resveratrol-treated group may be due to enhanced mitochondrial biogenesis mediated by SIRT1.	
Serious adverse events	- Renal failure with SRT501 (a micronized oral formulation of resveratrol) and bortezomid  - fever and bicytopenia 	12,14
Expected adverse events	- nausea and diarrhea	12,10,11,14
No adverse events discussed		15-31

Most studies did not show or discuss adverse events. Our study dosage at 125 mg/day for adults are far below these levels of 0.5 to 5 g per day which were associated with gastrointestinal distress.

### 2.3.2 KNOWN POTENTIAL BENEFITS

Numerous *in vitro* and *in vivo* studies have shown antioxidant and anti-inflammatory properties are associated with resveratrol administration. Since oxidative stress and inflammation play a important role in PSACH chondrocyte pathology, these antioxidant and anti-inflammatory properties may reduce joint pain in PSACH.

## 3 OBJECTIVES AND PURPOSE

To determine whether resveratrol treatment is effective in reducing pain in PSACH.

## 4 STUDY DESIGN AND ENDPOINTS

### 4.1 DESCRIPTION OF THE STUDY DESIGN

The study has a 2x2 crossover design. Participants will take either the placebo or resveratrol for 90 days followed by a 30 day washout period and the placebo or resveratrol for the last 90 days. 30 day washout period was chosen in order to eliminate any carry over from resveratrol as it is recommended to avoid resveratrol 2 weeks prior to surgery suggesting that carry over could potentially be as long as 2 weeks (<http://www.webmd.com/vitamins-supplements/ingredientmono-307-resveratrol.aspx?activeingredientid=307>; <http://ww5.komen.org/BreastCancer/Resveratrol.html>). Participants will be mailed a 30 or 90 day (for international participants) supply of placebo or resveratrol which they will receive 5 days before the end of each 30 day period (not applicable for international participants). Participants will keep daily pain log of pain and activity levels during the entire 210 day study period. We recognize that this is a long period of time however this population is highly motivated because 1) their pain is not systematically treated, 2) currently available over the counter NSAIDs, frequently used to control pain, cause gastrointestinal issues when used for prolonged periods and 3) participants reached through Little People of America and the PSACH facebook page are actively seeking solutions to control pain. This is being co-ordinated by a single center and will enroll 30 PSACH individuals. Because this is a rare condition, participants from 18 years - to 70 years will be enrolled.

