### 5.2 PARTICIPANT EXCLUSION CRITERIA

1. Current use of resveratrol
2. Current use of blood thinners, lovastatin, ketoconazole, itraconazole, fexofenadine and triazolam.
3. Other non-PSACH related health conditions, e.g. cancers.
4. Pregnancy or breastfeeding.
5. Women of childbearing age not using adequate contraception methods known to prevent pregnancy during the study.
6. Participation in another clinical study and/or using investigational agents.
7. Use of NSAIDs or aspirin.
8. Current use of Alfentanil, Cyclosporine, Dihydroergotamine, Dofetilide, Ergotamine, Fentanyl, Flibanserin, Oxycodone, Pimavanserin, Pimozide, Quinidine, Saquinavir, Sirolimus, Tacrolimus, Temsirolimus, Theophylline, Tizanidine, Thioridazine, Fosphenytoin, Phenytoin or Warfarin.
9. Age 17 years or less.
10. Platelet count below 50,000 per  $\mu\text{l}$  on baseline CBC.

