### 6.1.8 DOSE ADJUSTMENTS/MODIFICATIONS/DELAYS

N/A

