- Platelet count below 50,000 per  $\mu\text{l}$  will result in exclusion from the study as this increases risk of bleeding with injury. A normal platelet count is around 140,000 to 450,000 platelets per microliter ( $\mu\text{l}$ ) of blood. When the number of platelets is low, this concentration reduces. Women normally experience a platelet count that varies slightly during the menstrual cycle and can fall near the end of pregnancy. The risk of bleeding increases as the platelet count drops, but bleeding problems are unlikely unless the count is less than 80,000-100,000 platelets per  $\mu\text{l}$ .

The following platelet counts carry the risk of serious bleeding:

Between 20,000 and 50,000 per  $\mu\text{l}$ : There is more risk of bleeding when injured.

Less than 20,000 per  $\mu\text{l}$ : Bleeding happens even without injury.

Below 10,000 platelets per  $\mu\text{l}$ : Spontaneous bleeding can be severe and a risk to life.

---

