7.3.1 SCREENING/ENROLLMENT (VISIT 0)

- Review medical photos to confirm diagnosis of PSACH.
- Review medical history to determine eligibility based on inclusion/exclusion criteria.
- Review medications history to determine eligibility based on inclusion/exclusion criteria.
- Review urine pregnancy test to determine eligibility based on inclusion/exclusion criteria.
- Obtain written informed consent from participants which can be scanned/photographed and emailed to [contact].
- Inform participants of eligibility and enrollment into the study.
- Provide participants with specific instructions needed to participate in the study.
- Schedule phone visits for eligible participants for the duration of the study.

---

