### 7.3.3 FOLLOW-UP

#### **Follow-up Phone call (Visits 2, 3, 5, 6 and 7: Days 30, 60, 120, 150 and 180 +/- 5 working days)**

- Record adverse events as reported by participant to study co-ordinator. Study coordinator will ask about gastrointestinal health, any bleeding events and unusual bruising. PI will follow up with participant to assess the adverse events and determine whether to terminate participation.
- Record participant's adherence to treatment protocol.
- Inquire about any medication and health condition changes.
- Administer HRQoL instrument.
- Self-reported will be obtained from all study subjects using the Numeric Pain Rating Scale to score the subject's pain on a 0 to 10 scale. This scale has been validated and widely used. Pain will be ascertained daily (including during the "washout" period between the two intervention periods) through a daily pain log kept by participants. The pain logs will be requested from participants at each follow-up visit and at the end of each month in the treatment periods, and data from the pain logs will be compiled and analyzed at the start and end of each of the two treatment periods (on days 0, 90, 120, and 210).
- Request participant to mail back or email their pain log and a photo of the empty bottle at end of the month
- Inform participant to start on their next 30 days aliquot of study drug.

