**7.6 PROHIBITED MEDICATIONS, TREATMENTS, AND PROCEDURES**

Current use of resveratrol at time of study start (Day 0). Use of NSAIDs or aspirin. Blood thinners, lovastatin, ketoconazole, itraconazole, fexofenadine and triazolam. Alfentanil, Cyclosporine, Dihydroergotamine, Dofetilide, Ergotamine, Fentanyl, Flibanserin, Oxycodone, Pimavanserin, Pimozide, Quinidine, Saquinavir, Sirolimus, Tacrolimus, Temsirolimus, Theophylline, Tizanidine, Thioridazine, Fosphenytoin, Phenytoin or Warfarin.

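### Advice to avoid resveratrol for 2 weeks before surgery sets the washout, but the visible protocol does not apply it to participants who have an operation planned during the trial

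*Combined protocol and SAP*

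**What the plan says.** **The advice.** Section 4.1 explains the 30-day washout by noting that "it is recommended to avoid resveratrol 2 weeks prior to surgery", and infers that carry-over might last up to 2 weeks. The advice is used nowhere else in the visible text.

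**Surgery as a treatment.** Section 2.1 states: "The only treatments for this pain are sporadic NSAID administration and joint replacement". NSAIDs are excluded (5.2, item 7), so joint replacement is the only one of the two that a participant could still have.

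**Eligibility.** Inclusion criterion 2 in 5.1 tolerates complications of PSACH. None of the ten exclusions in 5.2 mentions surgery. The nearest, "Other non-PSACH related health conditions, e.g. cancers", concerns conditions unrelated to PSACH. Screening includes the step "Review medical history to determine eligibility based on inclusion/exclusion criteria", but there is no surgical criterion for that review to apply.

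**Product use.** Section 6.1.8, "DOSE ADJUSTMENTS/MODIFICATIONS/DELAYS", reads N/A. The heading of 7.6 covers procedures as well as medications, but its list holds only drugs and supplements; part of it reads "Use of NSAIDs or aspirin. Blood thinners, lovastatin, ketoconazole, itraconazole, fexofenadine and triazolam".

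**Bleeding.** The protocol already takes precautions here. Blood thinners are excluded (5.2). A platelet count below 50,000 per µl "will result in exclusion from the study as this increases risk of bleeding with injury" (7.1.1). At follow-up, "Study coordinator will ask about gastrointestinal health, any bleeding events and unusual bruising" (7.3.3).

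**The concern.** The protocol accepts a pre-surgical caution about its own study agent and enrols people for whom joint surgery is a recognised treatment. It then relies on the caution only for a pharmacological argument about carry-over. Under the visible rules, a person with a joint replacement booked inside the 210 days is eligible and may take study product up to the day of the operation.

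The protocol writes an explicit notify-and-stop rule where it sees a comparable uncertainty: in 8.4.5, participants who become pregnant must tell the team and stop product. Surgery has no equivalent. At stake is whether participants are dosed in a way that contradicts advice the protocol itself cites.

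**Working it through.** There is no figure in the plan to reproduce. The check is a reading of each section that could hold a surgery rule, followed by a day count.

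**1. Could another rule already stop product 2 weeks before an operation?**

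| Section | What it does | Why it falls short |
|---|---|---|
| 5.4.1(a) | The investigator may end participation for a medical condition or situation | Discretionary; surgery not named; ends participation instead of pausing product |
| 5.4.1(b) | Withdrawal for a newly met exclusion | No exclusion concerns surgery; it could act only if an excluded drug were started |
| 7.1.1, 7.3.3 | Calls about every 30 days ask about medication and health changes | Planned operations are not asked about |
| 7.8 | Removal if rescue medication does not control pain | Depends on pain, not on a booking |
| 8.5 | Participant stops product after one grade 3 AE | Needs an AE graded and recorded in time; surgery already booked at screening need not produce one |
| 8.4.5 | Notify and stop | Pregnancy only |

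Timing of the calls: suppose an operation is booked just after one call and is mentioned at the next, 30 days later. A full 14-day hold is then possible only if the notice was at least 30 + 14 = 44 days. Shorter notice can defeat the hold even when the participant volunteers the information. Monthly mailing is no check for international participants, who hold a 90-day supply (4.1, 6.1.10).

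**2. How often would resveratrol have been taken in the 14 days before an operation?**

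Inputs from the protocol: product on Days 0–90 and 120–210 (4.1, 6.1.9); avoidance interval 14 days (4.1); trial length 210 days.

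Assumptions, not in the documents: an operation falls with equal probability on any of the 210 days, product is taken as scheduled, and the two sequences are equally frequent.

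- Resveratrol first: operations on Days 0 to 90 + 14 = 104 qualify, so 104/210 = 0.495.
- Placebo first: operations on Days 120 to 210 qualify, so 90/210 = 0.429.
- Average: (0.495 + 0.429)/2 = 0.462, or about 46%.

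Counting either product, (104 + 90)/210 = 0.924. That figure includes placebo, so it describes how often a hold would change dosing and not how often resveratrol is involved.

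These fractions are conditional on an operation taking place. They follow from the dosing calendar and do not estimate risk.

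**3. What would a hold cost in dosing?** At most 14 of the 90 days in a period, 14/90 = 16%, before the operation.

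**The case against.** **Existing controls can act before some operations.** Section 8.3 records worsening of a PSACH problem as an AE, section 8.2.1 defines grade 3 to include hospitalization being indicated, and 8.5 stops product after one grade 3 AE. A joint that deteriorates on trial until inpatient surgery is indicated could therefore trigger a stop in time. This stands. The clearest remaining gap is surgery already booked at screening with no later deterioration, or with no AE recorded early enough.

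**Participants may be told elsewhere.** Section 7.3.1 says that participants receive instructions, and 13.3.1 says that the consent form describes agent and risks. Neither text is available to us. A reader might infer that participants are never told to stop before an operation; the documents do not support that, and the point is limited to the visible protocol body. A warning there would still not be an eligibility or dosing rule.

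**The harm is not shown.** A reader might infer an established operative bleeding risk. The protocol does not give the reason for the advice. Section 2.3.1 reports a 52-week trial at up to 2 g/day with no safety or tolerability difference from placebo except weight loss, against 125 mg/day here. The bleeding precautions make the omission relevant; they do not demonstrate harm at this dose.

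**Blinding.** A reader might infer that the assignment could not be learned before an operation. That is too strong: deterioration is an AE, and 10.6.3 lets the coordinator inform the DSMB if it considers this important. Unblinding is also unnecessary, because a hold can apply to either product.

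**Conclusion.** The inconsistency holds for the visible protocol. The advice in 4.1 is carried into neither 5.2 nor 6.1.8, and the partial safeguards do not reliably produce a 2-week stop. It is a low-cost safety improvement to consider.

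The size is uncertain. The documents give no rate of joint surgery, so the number of participants affected cannot be estimated. Given an operation on a random study day, about 46% (43% to 50% by sequence) would follow resveratrol use within 14 days, under the assumptions above.

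A reader might go further and infer that operations would bias the treatment comparison or cost material power. The documents do not support that. They give neither an operation rate nor a post-operative pain change, and the direction of any effect on a person's within-patient difference depends on the randomized sequence. The 2-unit threshold in 10.1 is also large against the variability assumed in 10.5. An SD of 10 to 15 on a 1–100 scale is about 1.0 to 1.5 here, so with 30 people the standard error is 1.0/√30 = 0.18 to 1.5/√30 = 0.27, and 2 units is about 7 to 11 standard errors. Even an assumed 4-point shift in one person's difference moves the mean by only 4/30 = 0.13.

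**What to change.** 1. Add to 5.2: *joint replacement or other elective surgery planned before Day 210*. Ask about it in the screening history (7.1.1, 7.3.1) and defer such candidates to a later enrolment.
2. Replace N/A in 6.1.8 with: *stop study product, whichever is assigned, at least 2 weeks before any planned operation, where timing allows; participants report an operation when it is booked and continue the pain log*.

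Surgery itself should not be prohibited in 7.6, since 2.1 names it as a treatment. An exclusion for recently completed surgery does not follow from pre-surgical advice and is not proposed.

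Cost: one eligibility line, one screening question and one rule in 6.1.8. A few of the 60 people to be screened (10.5) would be deferred and some might be lost, which matters in a rare disease. An operated participant would miss about 14 dosing days, plus any days off product after the operation.

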### 4.2.1 PRIMARY ENDPOINT

Self-reported pain will be obtained from all study subjects using the Numeric Pain Rating Scale to score the subject's pain on a 0 to 10 scale. This scale has been validated and widely used. A pain level will be assessed with enrollment in order to assure the participant has pain. An additional assessment will take place at the first visit (day 0). Pain will then be ascertained daily (including during the "washout" period between the two intervention periods) through a daily pain log kept by participants. The pain logs will be requested from participants at each follow-up visit and at the end of each month in the treatment periods, and data from the pain logs will be compiled and analyzed

at the start and end of each of the two treatment periods (on days 0, 90, 120, and 210). Monthly pain averages will be compared to baseline.

The primary endpoint will be change in pain score between baseline and monthly average pain scores. The pain score on each day of month one will be averaged to obtain the average pain score for month one, and the same will be done for months two and three, and each of the monthly average scores for resveratrol and placebo periods will be compared to baseline.

